#### **4.3.2 Prior and Concomitant Medication**

Prior and concomitant medications and concomitant non-drug treatment will be listed for the blinded data review.

### **4.4 Analysis of Efficacy**

#### **4.4.1 Primary Efficacy Endpoint**

##### **4.4.1.1 Primary Efficacy Endpoint Definition**

The primary endpoints are the dermatologist and ophthalmologist assessments of local tolerance through visual assessment of cutaneous (dermal response and superficial irritation) and ocular (conjunctiva involvement and lacrimal intensity) irritation scores/grades at Day 21.

This study will be considered a success if the majority (i.e. >50%) of subjects per treatment arm with combined dermatologist and ophthalmologist scores of zero at day 21 (+ 2).

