9.2.3. Criteria for Evaluation of Local Tolerance

The primary evaluation will be dermatologist and ophthalmologist visual assessments of local tolerance after 21 (+2) days of twice-daily study product application using the ITT population.

This study will be considered a success if the majority (i.e. >50%) of subjects per treatment arm complete the study with combined dermatologist and ophthalmologist scores of zero at day 21 (+ 2).

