9.2.5. Handling of Dropouts and Missing Data

Missing data will not be replaced or imputed. Dropouts will be included in analyses up to the point of discontinuation.

 GlaxoSmithKline	Document Name	Clinical Protocol 207782		
	Type	Version	Document Identifier	Effective Date
	eldo_clinical_doc	2.0; Most-Recent; Effective; CURRENT	090032d580d48db0	26-May-2017 05:53:15
	Reason For Issue	Auto Issue		

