### 1.4 Sample Size Calculation

A sufficient number of subjects will be screened (up to 170) to randomize approximately 92 subjects (46 per treatment group) to ensure that at least 40 subjects in each treatment group complete the study (80 subjects in total).

Randomization will be stratified by both contact lens wearer status (yes or no) and skin type (dry or normal/combination). The aim is to ensure balance of strata effects between treatment groups.

The sample size is based on clinical considerations to provide descriptive information on the tolerability and safety of the products, and is consistent with ANVISA guidelines (ANVISA, 2012).

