#### 4.1.3 Analysis Populations

Two analysis populations are defined.

Population	Definition / Criteria	Analyses Evaluated
Safety	
 
Comprises of all subjects for whom the lactic acid stinging test was performed.
 
This population will be based on the treatment the subject actually received.
 
	
 
Safety
 

Intent-To-Treat	
 
Comprises of all randomized subjects who have at least one cutaneous or ocular assessment following study product application.
 
This population will be based on the treatment the subject is randomised to.
 
	
 
Efficacy
 

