**Table 1 Changes to Protocol Defined Analysis Plan**

Protocol	Statistical Analysis Plan	Rationale for Changes

 
Section 2 – Objectives and Endpoints
 
	
 
Section 1.2 Study Objectives.
 
 
The dermatologist and ophthalmologist visual assessment of cutaneous and ocular irritation objective/endpoint at Day 1 has been added as a secondary objective.
	
 
For clarification that the Day 21 is the primary endpoint of interest, whereas the Day 1 results are of secondary importance.
 

 
Section 9.2.3 - Criteria for Evaluation of Local Tolerance.
 
 
“This study will be considered a success if the majority (i.e. >50%) of subjects per treatment arm complete the study with combined dermatologist and ophthalmologist scores of zero at day 21 (+ 2).”
	
 
Section 4.4.1.1 - Primary efficacy endpoint definition.
 
 
Reference to subjects completing the study has been removed.
	
 
Requirement for subjects to complete the study is not applicable when assessing the success of the study. This was specified in error in the protocol. The analysis population definition has no requirement for subjects to complete the study for evaluability.
 

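### Does the >50% success rule need a stated denominator for ITT subjects who have no Day 21 score?

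*SAP*

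**What the plan says.** Protocol 9.2.3 bases the primary evaluation on "visual assessments of local tolerance after 21 (+2) days of twice-daily study product application using the ITT population". It makes the study a success if the "majority (i.e. >50%) of subjects per treatment arm complete the study with combined dermatologist and ophthalmologist scores of zero" at the final visit.

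SAP 4.4.1.1 restates the rule as a "majority (i.e. >50%) of subjects per treatment arm with combined dermatologist and ophthalmologist scores of zero at day 21". SAP Section 5, Table 1 discloses the difference: "Reference to subjects completing the study has been removed". The reason given is that "The analysis population definition has no requirement for subjects to complete the study for evaluability".

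SAP 4.1.3 assigns efficacy to the ITT population, defined as "all randomized subjects who have at least one cutaneous or ocular assessment following study product application". Protocol 9.2.5 adds: "Missing data will not be replaced or imputed. Dropouts will be included in analyses up to the point of discontinuation".

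The shell for Table 14.2.1.1, which holds the deciding figure, is titled for the ITT population. It prints one ITT N at the head of each arm's n (%) column. It has no row for subjects not assessed at Day 21 and no note on the denominator.

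**The concern.** This is the trial's only decision rule, and neither the protocol nor the SAP writes out what the Day 21 percentage is divided by. ITT subjects without a Day 21 score can exist by design. The 1-hour assessment alone puts a subject in ITT, the schedule of events has no assessment between Visit 2 and Visit 3 or at early withdrawal, and Protocol 4.5 does not replace withdrawals.

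Two readings then seem open: zeros divided by all ITT subjects, or zeros divided by those assessed at Day 21. The second would favour the product if subjects stopped because of irritation, since they would leave the denominator. In a tolerance study that is the direction to worry about. The programming note to Table 14.1.1 states its denominators, which makes the silence in Table 14.2.1.1 more noticeable.

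**Working it through.** **Inputs.** SAP 1.4 plans to "randomize approximately 92 subjects (46 per treatment group) to ensure that at least 40 subjects in each treatment group complete the study". The threshold is strictly above 50% (Protocol 9.2.3, SAP 4.4.1.1). Neither document states a zero-score rate or a dropout rate.

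**The plan's own figures.** 2 × 46 = 92 and 2 × 40 = 80. The allowance for loss is 46 − 40 = 6 per arm, or 6/46 = 13.0%. There is no alpha, power or effect size to reproduce, because the sample size rests on clinical considerations.

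**Zeros needed.** For a denominator n, the smallest count strictly above half is floor(n/2) + 1. Assume all 46 randomised subjects in the arm are in ITT. Then the ITT reading always needs floor(46/2) + 1 = 24, because 23/46 is exactly 50.0% and fails.

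| Assessed at Day 21 | Zeros needed, assessed reading | Counts on which the readings disagree | 24 zeros as a share of assessed |
|---|---|---|---|
| 45 | 23 | 23 | 53.3% |
| 44 | 23 | 23 | 54.5% |
| 43 | 22 | 22, 23 | 55.8% |
| 42 | 22 | 22, 23 | 57.1% |
| 41 | 21 | 21, 22, 23 | 58.5% |
| 40 | 21 | 21, 22, 23 | 60.0% |

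With 40 assessed, 21, 22 and 23 zeros are 52.5%, 55.0% and 57.5% of those assessed, but 45.7%, 47.8% and 50.0% of ITT. With nobody missing the two readings are the same. With up to six missing they agree whenever at least 60% of assessed subjects score zero.

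**Chance of opposite calls in one arm.** Let X be the number of zeros among a assessed subjects, binomial with an assumed true zero rate p. The chance is P(X ≥ floor(a/2) + 1) − P(X ≥ 24).

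| p | 40 assessed | 43 assessed | 45 assessed |
|---|---|---|---|
| 0.60 | 0.870 − 0.568 = 0.302 | 0.909 − 0.764 = 0.144 | 0.057 |
| 0.70 | 0.994 − 0.937 = 0.057 | 0.997 − 0.984 = 0.013 | 0.004 |
| 0.75 | 0.011 | 0.002 | <0.001 |
| 0.80 | 0.001 | 0.0001 | <0.0001 |

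If both arms must pass, with equal rates and 40 assessed in each, the success probabilities (assessed reading, then ITT reading) are 0.870² = 0.76 and 0.568² = 0.32 at p = 0.60. They are 0.99 and 0.88 at 0.70, and >0.999 and 0.998 at 0.80.

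**What the text supports.** Four things point to the ITT number:
- the rule counts subjects per treatment arm;
- Protocol 9.2.3 names ITT for this evaluation;
- SAP 4.1.3 assigns efficacy to ITT;
- the deciding table carries the ITT N above its percentages.

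On the other side stands Protocol 9.2.5. It forbids filling in scores and keeps dropouts only until they leave, but it does not mention the denominator of the success percentage. Leaving a subject in N without a score imputes nothing.

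**The case for a change.** The strongest argument for acting is that a trial's only success criterion should be fixed in words before anyone sees the result. Being able to recover both percentages afterwards does not say which one decides. The disagreement is not negligible in every scenario: at a true zero rate of 60% with six subjects missing, one arm's call depends on the denominator about 30% of the time. Removing the completion wording also took away the phrase that most nearly said a success needs an observed Day 21 zero. A clarifying sentence would cost almost nothing.

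The arithmetic stands, and so does the observation that the handling of a missing Day 21 score is not spelled out. Three things weaken the call for a change. First, the documents already lean clearly to the ITT number. Second, a rule that expressly counts every missing subject as a non-success would go beyond clarification: it would partly restore a completion requirement that SAP Section 5 removed as an error, and the sponsor's statistician could reasonably dispute it. Third, SAP Addendum 1 was written after unblinding and left the rule alone, so new wording could not restore prespecification.

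**Conclusion.** The concern does not call for a change to the plan. The gap is real but small: an ITT subject without a Day 21 score is not mentioned, and the stated population and table layout lead an analyst to divide by the ITT number. The choice affects the call only when several subjects in an arm lack Day 21 data and the zero rate is near 50–60%. In the planned-minimum case that means exactly 21, 22 or 23 zeros. At zero rates of about 75–80% or more, the chance of opposite calls is about 0.01 or less per arm, and the reported percentage differs by a factor of at most 46/40 = 1.15.

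These sizes assume that all 46 per arm enter ITT and that at least 40 are assessed. The zero rates are illustrative. The consequences are limited further because no formal inference is planned. The tables give the zero counts and the ITT N, and Listings 16.2.6.1 and 16.2.1.1 give scores by visit and withdrawal reasons. A reader can therefore compute both percentages and see whether irritation drove any losses.

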##### **Calculation of combined dermatologist score (dermal response and superficial irritation):**

The combined dermatologist score will be calculated in the following way:

Combined score = dermal response score + numerical equivalent of the superficial irritation score

Where, the dermal response scale is described in the Table 1 below, and the superficial irritation scores in Table 2 below.

[figure not shown]
Micellar Cleanser

207782

Draft Statistical Reporting and Analysis plan Amendment #1, 14 Aug 2017

---

CCI

CCI

Micellar Cleanser

[figure not shown]
207782

Draft Statistical Reporting and Analysis plan Amendment #1, 14 Aug 2017

CCI

CCI

#### **4.4.1.2 Statistical Hypothesis, Model, and Method of Analysis**

No formal statistical inference will be performed.

The combined dermatologist and ophthalmologist score will be summarized using frequencies and percentages by treatment group and time point, with Day 21 results of primary interest. The sum across post-baseline observations for the combined dermatologist and

ophthalmologist score will also be summarized using frequencies and percentages by treatment group.

Similar summaries will also be provided for the following variables:

[figure not shown]
- Combined dermatologist and ophthalmologist score (modified) = dermal response score + conjunctiva involvement score + lacrimal intensity score
- Combined dermatologist score
- Combined ophthalmological score
- Dermal response score
- Conjunctiva involvement score
- Lacrimal intensity score

Data will also be presented by sub-groups (strata), contact lens wearer status (not contact lens wearer, contact lens wearer) and skin type (dry, normal/combination) by the following categories:

- Not contact lens wearer with dry skin
- Contact lens wearer with dry skin
- Not contact lens wearer with normal/combination skin
- Contact lens wearer with normal/combination skin.

#### **4.4.2 Secondary Efficacy Variables**

CCI

## 4.5 Analysis of Secondary Objectives

### 4.5.1 Efficacy (Secondary)

The secondary endpoints will be summarized in the same way as the primary endpoints. Each subject assessment (redness, dryness, burning, itching and stinging) and combined score (summed across these 5 assessments) will be presented at each time point separately for eyes and face. The sum across post-baseline observations will also be summarized in the same way.

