3. STUDY PLAN

3.1. Study Design

Overall Design

This is an assessor blind (dermatologist and ophthalmologist) clinical in use study to determine the local cutaneous and ocular tolerance of two cosmetic facial cleanser products when used as per the intended instructions for use in a population of healthy female subjects with clinically assessed sensitive skin.
 
Subjects who have sensitive skin as classified by a positive reaction to a lactic acid Stinging Test will be asked to use one of two cleansing products as part of their normal skin care routine for 3 weeks.
 
Both test products are the same formulation but are differentiated by the dispensing pack; to either a micellar cleanser or a foaming cleanser.
 
Subjects will be instructed to cleanse their face with one of the two test products at home twice-daily, for 21 (+ 2) days, including a supervised first application at the study site (Visit 2) and a final application at home on the morning of the final visit (Visit 3), as per the intended instructions for use.

 GlaxoSmithKline	Document Name	Clinical Protocol 207782		
	Type	Version	Document Identifier	Effective Date
	eldo_clinical_doc	2.0; Most-Recent; Effective; CURRENT	090032d580d48db0	26-May-2017 05:53:15
	Reason For Issue	Auto Issue		

A qualified dermatologist and a qualified ophthalmologist will assess the baseline cutaneous and ocular irritation of prospective subjects at Visit 2. For a subject to be considered eligible to participate in the study, all dermatologist and ophthalmologist assessment scores must be zero. Further dermatologist and ophthalmologist assessments will be completed 1-hour (\pm 20 minutes) post supervised first product use and at the final visit (Visit 3) at the end of the 21 (+2) day product use period. The intensity of any visual signs of cutaneous and ocular irritation will be recorded by the dermatologist and ophthalmologist, according to the assessment scales detailed in Appendix 3 and 4.

The dermatologist will also determine each subject's facial skin type as dry, oily or normal/combination skin. Any subject classified as having oily skin will not be considered eligible for participation in the study as they do not represent the target population for the product.

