6.2.7. Subject self-assessment

Subjects will be asked to answer the self-assessment question as per Appendix 5 prior to any product use.

 GlaxoSmithKline	Document Name	Clinical Protocol 207782		
	Type	Version	Document Identifier	Effective Date
	eldo_clinical_doc	2.0; Most-Recent; Effective; CURRENT	090032d580d48db0	26-May-2017 05:53:15
	Reason For Issue	Auto Issue		

The self-assessment questions will be asked again 1 hour (\pm 20 minutes) following first supervised test product use. Additionally, a final assessment at Visit 3 will be completed at the end of the 21 (+2) day product use period.

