6.3. Visit 3 - Last Subject Last Visit (LSLV) and Study Conclusion

Subjects will return to the study site after 21 (+ 2) days of twice daily product use. Subjects will return their test products and diary card. The diary card will be reviewed to check compliance and evaluate subject comments. The total number of product applications and total number of missed product applications will be recorded in the CRF.

Final dermatologist (per section 6.2.5) and ophthalmologist (per section 6.2.6) assessments will be completed and the subject will answer the self-assessment questions (Appendix 5) based on their experience of using the product.

 GlaxoSmithKline	Document Name	Clinical Protocol 207782		
	Type	Version	Document Identifier	Effective Date
	eldo_clinical_doc	2.0; Most-Recent; Effective; CURRENT	090032d580d48db0	26-May-2017 05:53:15
	Reason For Issue	Auto Issue		

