## **3 Considerations for data analyses and Data Handling Conventions**

### **3.1 Baseline Definition**

For all endpoints the baseline value will be the latest pre-treatment assessment with a non-missing value.

Unless otherwise stated, if baseline data is missing no derivation will be performed and will be set to missing.

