**Programming Note:**

Micellar Cleanser

207782

Draft Statistical Reporting and Analysis plan Amendment #1, 14 Aug 2017

---

- This table shell is used for Table 14.2.5.2 as well. Add "Strata: NOT contact lens wearer with Dry skin" etc. below the line "Intent to Treat Population (N=XX)".

Micellar Cleanser

207782

Draft Statistical Reporting and Analysis plan Amendment #1, 14 Aug 2017

Protocol: 207782

Program Run Date:ddmonyyyy

Table 14.2.8.1  
Frequency of Subject Assessment Scores for Eyes  
Intent to Treat Population

Intent to Treat Population (N=XX)

Assessment: Redness

Timepoint	Micellar Cleanser	Micellar Foaming Cleanser
	(N=XX)	(N=XX)
	n (%)	n (%)
BASELINE		
0/NONE	xx (xx.xx)	xx (xx.xx)
1/MILD	xx (xx.xx)	xx (xx.xx)
2/MODERATE	xx (xx.xx)	xx (xx.xx)
3/SEVERE	xx (xx.xx)	xx (xx.xx)
1 HOUR		
0/NONE	xx (xx.xx)	xx (xx.xx)
1/MILD	xx (xx.xx)	xx (xx.xx)
2/MODERATE	xx (xx.xx)	xx (xx.xx)
3/SEVERE	xx (xx.xx)	xx (xx.xx)
DAY 21		
0/NONE	xx (xx.xx)	xx (xx.xx)
1/MILD	xx (xx.xx)	xx (xx.xx)
2/MODERATE	xx (xx.xx)	xx (xx.xx)
3/SEVERE	xx (xx.xx)	xx (xx.xx)
SUM OF POST-BASELINE REDNESS SCORES		
.....	xx (xx.xx)	xx (xx.xx)

PPD

Programming Note: Repeat for Dryness, Burning, Itching and Stinging. This shell will also be used for table 14.2.9.1.

Page X of Y

Micellar Cleanser

207782

Draft Statistical Reporting and Analysis plan Amendment #1, 14 Aug 2017

Protocol: 207782

Program Run Date:ddmonyyyy

Table 14.2.8.2  
Frequency of Subject Assessment Combined Score\* for Eyes  
Intent to Treat Population

Intent to Treat Population (N=XX)

Timepoint	Micellar Cleanser	Micellar Foaming Cleanser
	(N=XX)	(N=XX)
	n (%)	n (%)
BASELINE		
0	xx (xx.xx)	xx (xx.xx)
1	xx (xx.xx)	xx (xx.xx)
...	xx (xx.xx)	xx (xx.xx)
15	xx (xx.xx)	xx (xx.xx)
1 HOUR		
0	xx (xx.xx)	xx (xx.xx)
1	xx (xx.xx)	xx (xx.xx)
...	xx (xx.xx)	xx (xx.xx)
15	xx (xx.xx)	xx (xx.xx)
DAY 21		
0	xx (xx.xx)	xx (xx.xx)
1	xx (xx.xx)	xx (xx.xx)
...	xx (xx.xx)	xx (xx.xx)
15	xx (xx.xx)	xx (xx.xx)
SUM OF POST-BASELINE COMBINED SCORE* FOR EYES		
.....	xx (xx.xx)	xx (xx.xx)

\* Combined score for eyes is obtained by summing the 5 subject assessments for eyes i.e. redness, dryness, burning, itching and stinging.

PPD

Programming Note:This shell will also be used for table 14.2.9.2 (same footnote applies).

Page X of Y

Micellar Cleanser

207782

Draft Statistical Reporting and Analysis plan Amendment #1, 14 Aug 2017

Protocol: 207782

Program Run Date: ddmmmyyyy

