**Programming Note: Please include the sum of post baseline scores.**

Micellar Cleanser

207782

Draft Statistical Reporting and Analysis plan Amendment #1, 14 Aug 2017

---

Protocol: 207782

Program Run Date: DDMMYYYY

Listing 16.2.6.2.1  
Subject Self-Assessment (Face)  
All Randomised Subjects

Treatment Group: Micellar Cleanser

Subject	Sex/Age/ Race [1]	Visit	Visit Date	Redness	Dryness	Burning	Itching	Stinging	Combined Score
PPD									
...									

[1] Age in years; Sex: F = Female, M = Male; Race: A = Asian, B = Black or African American, I = American Indian or Alaska Native, H = Native Hawaiian or Other Pacific Islander, W = White, M = Multiple.

Page x of y

PPD

Programming Note: Please include the sum of post baseline scores.

Micellar Cleanser

207782

Draft Statistical Reporting and Analysis plan Amendment #1, 14 Aug 2017

---

Protocol: 207782

Program Run Date: DDMMYYYY

Listing 16.2.6.2.2  
Subject Self-Assessment (Eye)  
All Randomised Subjects

Treatment Group: Micellar Cleanser

Subject	Sex/Age/ Race [1]	Visit	Visit Date	Redness	Dryness	Burning	Itching	Stinging	Combined Score
PPD									

[1] Age in years; Sex: F = Female, M = Male; Race: A = Asian, B = Black or African American, I = American Indian or Alaska Native, H = Native Hawaiian or Other Pacific Islander, W = White, M = Multiple.

PPD

Page x of y

Programming Note: Please include the sum of post baseline scores.

Micellar Cleanser

207782

Draft Statistical Reporting and Analysis plan Amendment #1, 14 Aug 2017

Protocol: 207782

Program Run Date: DDMMYYYY

Listing 16.2.7.1

All Adverse Events

All Randomized Subjects

Treatment Group: Micellar Cleanser

Subject	Sex/Age/ Race [1]	Adverse Event (Preferred Term) [System Organ Class]	Start Date (Study Day) [2]	Start Time	End Date	End Time	Frequency/ Intensity [3]	Related to Study Product?	Action Taken Re Study Product	Withdraw?
PPD										
....										

[1] Age in years; Sex: F = Female, M = Male; Race: A = Asian, B = Black or African American, I = American Indian or Alaska Native, H = Native Hawaiian or Other Pacific Islander, W = White, M = Multiple.

[2] Study day is the day relative to start of treatment, day 1 being the day of first treatment.

[3] INT = Intermittent and SGLE = Single.

[4] Did subject withdraw from study as a result of this adverse event?

PPD

Page x of y

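### No planned table counts subjects whose self-assessed symptoms rose above their own baseline, and the raw post-baseline sum does not separate stable from new symptoms

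*SAP*

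**What the plan says.** Protocol section 3.1 makes entry conditional on clinician findings: "all dermatologist and ophthalmologist assessment scores must be zero". Inclusion criteria 5c and 5d (Protocol 4.1) repeat this. No criterion limits the self-assessment score.

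Protocol 6.2.7 has the self-assessment taken before treatment: "Subjects will be asked to answer the self-assessment question as per Appendix 5 prior to any product use". The questions are repeated 1 hour after the supervised application and at Visit 3, where Protocol 6.3 says the answers are "based on their experience of using the product".

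SAP 3.1 defines a baseline: "For all endpoints the baseline value will be the latest pre-treatment assessment with a non-missing value".

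SAP 4.5.1 carries the primary endpoint's summary method over to the five self-assessed items and their combined score, for eyes and face separately, and adds: "The sum across post-baseline observations will also be summarized in the same way". The SAP table list gives four outputs, Tables 14.2.8.1, 14.2.8.2, 14.2.9.1 and 14.2.9.2, all frequency tables. The item shell in SAP section 8 has blocks for Baseline, 1 Hour and Day 21, each with grades 0 to 3, and a closing block headed "SUM OF POST-BASELINE REDNESS SCORES" (repeated for the other items). The notes to Listings 16.2.6.2.1 and 16.2.6.2.2 say: "Please include the sum of post baseline scores". No self-assessment table has a change, shift or worsening row.

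**The concern.** The method suits the clinician scores because every eligible subject starts at zero, so any later non-zero score is new. That premise does not hold for self-assessment. The sponsor's own shells provide baseline rows up to grade 3 per item and 15 for the combined score. The population also makes non-zero starting values plausible: Protocol section 1 describes sensitive skin by stinging, burning or itching, and dry skin is a randomisation stratum.

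The study is non-comparative (Protocol 3.4), so no untreated arm shows the background level of symptoms. Comparison with the subject's own pre-use answer is the most direct evidence of whether a reported symptom began or worsened during use. Baseline is collected and defined, but no planned table uses it in that way. A report built from these tables could show identical Baseline and Day 21 columns while some subjects worsened and as many others improved.

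**Working it through.** There is no planned figure to reproduce: the documents give no baseline symptom rate, and no formal inference is planned (SAP 4.4.1.2). The check asks what the planned rows can and cannot distinguish.

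**Inputs.** Item grades 0 to 3 and combined score 0 to 15, since 5 × 3 = 15 (SAP section 8 shells). 46 randomised per arm and at least 40 completers per arm (SAP 1.4). The symptom rates below are assumptions.

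**1. Two constructed data sets with identical planned rows.** One arm, one item, 40 subjects; scores are ordered Baseline, 1 Hour, Day 21.

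- Set A: 20 subjects score (1,1,1) and 20 score (0,0,0).
- Set B: 20 subjects score (1,0,0) and 20 score (0,1,1).

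| Row | Set A | Set B |
|---|---|---|
| Baseline: score 0 / score 1 | 20 / 20 | 20 / 20 |
| 1 Hour: score 0 / score 1 | 20 / 20 | 20 / 20 |
| Day 21: score 0 / score 1 | 20 / 20 | 20 / 20 |
| Post-baseline sum: 0 / 2 | 20 / 20 | 20 / 20 |
| Day 21 above own baseline (not planned) | 0/40 (0%) | 20/40 (50%) |

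Every planned row agrees. Only the unplanned one separates the sets.

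**2. How wide the ambiguity can be.** For a symptom scored 0 or 1, let b be the number with it at Baseline, d the number at Day 21 and n the arm size. The number worsened lies between max(0, d − b) and min(d, n − b). With d = b = k this becomes 0 to min(k, n − k). For n = 46:

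| Assumed rate at both times | k | Possible number worsened |
|---|---|---|
| 0% | 0 | 0 |
| 10% | 5 | 0 to 5 |
| 30% | 14 | 0 to 14 |
| 50% | 23 | 0 to 23 |

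At 0% the ambiguity vanishes, which is why the clinician scores do not share the problem.

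**3. What the raw sum hides.** An item sum of 2 arises from three (1 Hour, Day 21) pairs: (0,2), (1,1) and (2,0). With four possible baselines there are 3 × 4 = 12 patterns. Day 21 compared with Baseline:

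| Pair | Higher | Equal | Lower |
|---|---|---|---|
| (0,2) | 2 | 1 | 1 |
| (1,1) | 1 | 1 | 2 |
| (2,0) | 0 | 1 | 3 |
| Total | 3 | 3 | 6 |

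For example, (0,1,1), (1,1,1) and (2,1,1) all give a sum of 2. The enumeration shows what is possible, not how often each pattern occurs.

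**The case against.** The strongest reply is that the plan answers the endpoint as defined: self-assessment responses after 21 days, a level rather than a change. Nothing in the Protocol or SAP promises a shift analysis, and SAP 3.1 may only say which value fills the Baseline row. Baseline frequencies sit beside the later ones, so net shift is visible, and with about 46 subjects per arm the listings allow a hand count.

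There is also an adverse event route. Symptoms are asked about at each visit (Protocol 7.4), diary comments are reviewed (6.3.1), and subjects are told to contact the site about reactions (6.2.9). The rule that gradable responses are not adverse events (7.1.1) names the stinging test and Appendices 3 and 4, not Appendix 5.

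The rates above are assumed, and the upper bounds need complete turnover between affected and unaffected subjects. Entry rules such as clinician scores of zero and exclusion of active dermatosis may keep baseline symptoms low. Appendix 5 is not in the supplied text and SAP 4.4.2 is redacted, so the pre-use and Visit 3 questions may not be on the same footing. Finally, counting only increases is one-sided, and without a control it does not attribute them to the product.

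Most of this stands as a limit on the weight of the point. It does not supply the missing count. A listing is not a summary, net change is not the number of subjects affected, and adverse event tables capture worsening only when it is recorded as an event, on a different severity scale. The redaction does not alter the readable table list and shells. Shift tables show both directions for the items; the combined score would still have only an above-baseline count, a minor gap in a tolerance study.

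**Conclusion.** The concern holds. Self-assessment baselines may be non-zero, no planned table counts subjects who worsened from their own baseline, and the raw post-baseline sum does not separate stable, new and improving symptoms. In the constructed example, identical planned rows fit 0 of 40 or 20 of 40 worsened. With 46 per arm and equal rates at Baseline and Day 21, the possible numbers run to 5, 14 or 23 at assumed rates of 10%, 30% and 50%.

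The practical size depends on the actual baseline symptom rate, which the documents do not give, and on whether the pre-use and Visit 3 questions are comparable. The endpoint is secondary and descriptive, and the success criterion (Protocol 9.2.3, SAP 4.4.1.1) uses clinician scores only. This is an inexpensive improvement that should be made; it does not threaten the study's main conclusion.

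**What to change.** For each of the five items, face and eyes separately, add by arm the number and percentage of subjects scoring above their own SAP 3.1 baseline at 1 hour and at Day 21, among subjects with both values. Support these with 4×4 shift tables of baseline grade by grade at each time point. For the combined score (0 to 15), give only the number and percentage above baseline. Keep the planned post-baseline sum, labelled as not baseline-adjusted.

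No new data are needed. The counts come to 6 scores × 2 sites × 2 time points = 24 lines per arm, which fit in one table. The shift tables come to 5 × 2 × 2 = 20 small grids per arm, suitable for an appendix.

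The costs are extra descriptive output and post hoc status: SAP Addendum 1 already postdates unblinding (its section 1), so additions made now should be labelled post hoc. Before interpreting the counts, compare the Appendix 5 wording for the pre-use and Visit 3 questions, and state any difference beside the table.
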